5 WARNINGS AND PRECAUTIONS

5.1 Hypertension

In Study 1 hypertension was reported in 73% of LENVIMA-treated patients and 16% of patients in the placebo group [*see Adverse Reactions (6.1)*]. The median time to onset of new or worsening hypertension was 16 days for LENVIMA-treated patients. The incidence of Grade 3 hypertension was 44% as compared to 4% for placebo, and the incidence of Grade 4 hypertension was less than 1% in LENVIMA-treated patients and none in the placebo group.

Control blood pressure prior to treatment with LENVIMA. Monitor blood pressure after 1 week, then every 2 weeks for the first 2 months, and then at least monthly thereafter during treatment with LENVIMA. Withhold LENVIMA for Grade 3 hypertension despite optimal antihypertensive therapy; resume at a reduced dose when hypertension is controlled at less than or equal to Grade 2. Discontinue LENVIMA for life-threatening hypertension [*see Dosage and Administration (2.2)*].

5.2 Cardiac Dysfunction

In Study 1, cardiac dysfunction, defined as decreased left or right ventricular function, cardiac failure, or pulmonary edema, was reported in 7% of LENVIMA-treated patients (2% Grade 3 or greater) and 2% (no Grade 3 or greater) of patients in the placebo group. The majority of these cases in LENVIMA-treated patients (14 of 17 cases) were based on findings of decreased ejection fraction as assessed by echocardiography. Six of 261 (2%) LENVIMA-treated patients in Study 1 had greater than 20% reduction in ejection fraction as measured by echocardiography compared to no patients who received placebo.

Monitor patients for clinical symptoms or signs of cardiac decompensation. Withhold LENVIMA for development of Grade 3 cardiac dysfunction until improved to Grade 0 or 1 or baseline. Either resume at a reduced dose or discontinue LENVIMA depending on the severity and persistence of cardiac dysfunction. Discontinue LENVIMA for Grade 4 cardiac dysfunction [*see Dosage and Administration (2.2)*].

5.3 Arterial Thromboembolic Events

In Study 1, arterial thromboembolic events were reported in 5% of LENVIMA-treated patients and 2% of patients in the placebo group. The incidence of arterial thromboembolic

events of Grade 3 or greater was 3% in LENVIMA-treated patients and 1% in the placebo group.

Discontinue LENVIMA following an arterial thrombotic event. The safety of resuming LENVIMA after an arterial thromboembolic event has not been established and LENVIMA has not been studied in patients who have had an arterial thromboembolic event within the previous 6 months [*see Dosage and Administration (2.2)*].

5.4 Hepatotoxicity

In Study 1, 4% of LENVIMA-treated patients experienced an increase in alanine aminotransferase (ALT) and 5% experienced an increase in aspartate aminotransferase (AST) that was Grade 3 or greater. No patients in the placebo group experienced Grade 3 or greater increases in ALT or AST. Across clinical studies in which 1108 patients received LENVIMA, hepatic failure (including fatal events) was reported in 3 patients and acute hepatitis was reported in 1 patient.

Monitor liver function before initiation of LENVIMA, then every 2 weeks for the first 2 months, and at least monthly thereafter during treatment. Withhold LENVIMA for the development of Grade 3 or greater liver impairment until resolved to Grade 0 to 1 or baseline. Either resume at a reduced dose or discontinue LENVIMA depending on the severity and persistence of hepatotoxicity. Discontinue LENVIMA for hepatic failure [*see Dosage and Administration (2.2)*].

5.5 Proteinuria

In Study 1, proteinuria was reported in 34% of LENVIMA-treated patients and 3% of patients in the placebo group [*see Adverse Reactions (6.1)*]. The incidence of Grade 3 proteinuria in LENVIMA-treated patients was 11% compared to none in the placebo group.

Monitor for proteinuria before initiation of, and periodically throughout treatment. If urine dipstick proteinuria greater than or equal to 2+ is detected, obtain a 24 hour urine protein. Withhold LENVIMA for ≥ 2 grams of proteinuria/24 hours and resume at a reduced dose when proteinuria is < 2 gm/24 hours. Discontinue LENVIMA for nephrotic syndrome [*see Dosage and Administration (2.2)*].

5.6 Renal Failure and Impairment

In Study 1, events of renal impairment were reported in 14% of LENVIMA-treated patients compared to 2% of patients in the placebo group. The incidence of Grade 3 or greater renal failure or impairment was 3% in LENVIMA-treated patients and 1% in the placebo group. The primary risk factor for severe renal impairment in LENVIMA-treated patients was dehydration/hypovolemia due to diarrhea and vomiting.

Withhold LENVIMA for development of Grade 3 or 4 renal failure/impairment until resolved to Grade 0 to 1 or baseline. Either resume at a reduced dose or discontinue LENVIMA depending on the severity and persistence of renal impairment [*see Dosage and Administration (2.2)*].

5.7 Gastrointestinal Perforation and Fistula Formation

In Study 1, events of gastrointestinal perforation or fistula were reported in 2% of LENVIMA-treated patients and 0.8% of patients in the placebo group.

Discontinue LENVIMA in patients who develop gastrointestinal perforation or life-threatening fistula [*see Dosage and Administration (2.2)*].

5.8 QT Interval Prolongation

In Study 1, QT/QTC interval prolongation was reported in 9% of LENVIMA-treated patients and 2% of patients in the placebo group. The incidence of QT interval prolongation of Grade 3 or greater was 2% in LENVIMA-treated patients compared to no reports in the placebo group. Monitor electrocardiograms in patients with congenital long QT syndrome, congestive heart failure, bradyarrhythmias, or those who are taking drugs known to prolong the QT interval, including Class Ia and III antiarrhythmics.

Monitor and correct electrolyte abnormalities in all patients. Withhold LENVIMA for the development of Grade 3 or greater QT interval prolongation. Resume LENVIMA at a reduced dose when QT prolongation resolves to Grade 0 or 1 or baseline [*see Dosage and Administration (2.2), Clinical Pharmacology (12.2)*].

5.9 Hypocalcemia

In Study 1, 9% of LENVIMA-treated patients experienced Grade 3 or greater hypocalcemia compared to 2% in the placebo group. In most cases hypocalcemia responded to replacement and dose interruption/dose reduction [*see Adverse Reactions (6.1)*].

Monitor blood calcium levels at least monthly and replace calcium as necessary during LENVIMA treatment. Interrupt and adjust LENVIMA dosing as necessary depending on severity, presence of ECG changes, and persistence of hypocalcemia [*see Dosage and Administration (2.2)*].

Across clinical studies in which 1108 patients received LENVIMA, Grade 3 or greater hemorrhage was reported in 2% of patients. In Study 1, there was 1 case of fatal intracranial hemorrhage among 16 patients who received lenvatinib and had CNS metastases at baseline.

Withhold LENVIMA for the development of Grade 3 hemorrhage until resolved to Grade 0 to 1. Either resume at a reduced dose or discontinue LENVIMA depending on the severity and persistence of hemorrhage. Discontinue LENVIMA in patients who experience Grade 4 hemorrhage [*see Dosage and Administration (2.2)*].

5.12 Impairment of Thyroid Stimulating Hormone Suppression

LENVIMA impairs exogenous thyroid suppression. In Study 1, 88% of all patients had a baseline thyroid stimulating hormone (TSH) level less than or equal to 0.5 mU/L. In those patients with a normal TSH at baseline, elevation of TSH level above 0.5 mU/L was observed post baseline in 57% of LENVIMA-treated patients as compared with 14% of patients receiving placebo.

Monitor TSH levels monthly and adjust thyroid replacement medication as needed in patients with DTC.

5.13 Embryofetal Toxicity

Based on its mechanism of action and data from animal reproduction studies, LENVIMA can cause fetal harm when administered to a pregnant woman. In animal reproduction studies, oral administration of lenvatinib during organogenesis at doses below the recommended human dose resulted in embryotoxicity, fetotoxicity, and teratogenicity in rats and rabbits. Advise pregnant women of the potential risk to a fetus. Advise females of reproductive potential to use effective contraception during treatment with LENVIMA and for at least 2 weeks following completion of therapy [*see Use in Specific Populations (8.1, 8.3)*].

5.10 Reversible Posterior Leukoencephalopathy Syndrome

Across clinical studies in which 1108 patients received LENVIMA, there were 3 reported events of reversible posterior leukoencephalopathy syndrome (RPLS). Confirm the diagnosis of RPLS with MRI. Withhold for RPLS until fully resolved. Upon resolution, resume at a reduced dose or discontinue LENVIMA depending on the severity and persistence of neurologic symptoms [*see Dosage and Administration (2.2)*].

5.11 Hemorrhagic Events

In Study 1, hemorrhagic events occurred in 35% of LENVIMA-treated patients and in 18% of the placebo group. However, the incidence of Grade 3-5 hemorrhage was similar between arms at 2% and 3%, respectively. The most frequently reported hemorrhagic event was epistaxis (11% Grade 1 and 1% Grade 2). Discontinuation due to hemorrhagic events occurred in 1% of LENVIMA-treated patients.

- Impairment of Thyroid Stimulating Hormone Suppression

6 ADVERSE REACTIONS

The following adverse reactions are discussed elsewhere in the label:

- Hypertension [*see Warnings and Precautions (5.1)*]
- Cardiac Dysfunction [*see Warnings and Precautions (5.2)*]
- Arterial Thromboembolic Events [*see Warnings and Precautions (5.3)*]
- Hepatotoxicity [*see Warnings and Precautions (5.4)*]
- Proteinuria [*see Warnings and Precautions (5.5)*]
- Renal Failure and Impairment [*see Warnings and Precautions (5.6)*]
- Gastrointestinal Perforation and Fistula Formation [*see Warnings and Precautions (5.7)*]
- QT Interval Prolongation [*see Warnings and Precautions (5.8)*]
- Hypocalcemia [*see Warnings and Precautions (5.9)*]
- Reversible Posterior Leukoencephalopathy Syndrome [*see Warnings and Precautions (5.10)*]
- Hemorrhagic Events [*see Warnings and Precautions (5.11)*]

6.1 Clinical Trials Experience

Because clinical trials are conducted under widely varying conditions, adverse reaction rates observed in the clinical trials of a drug cannot be directly compared to rates in the clinical trials of another drug and may not reflect the rates observed in practice.

Safety data obtained in 1108 patients with advanced solid tumors who received LENVIMA as a single agent across multiple clinical studies was used to further characterize risks of serious adverse drug reactions [*see Warnings and Precautions (5.4, 5.10, 5.11)*]. The median age was 60 years (range 21-89 years). The dose range was 0.2 mg to 32 mg. The median duration of exposure in the entire population was 5.5 months.

The safety data described below are derived from Study 1 which randomized (2:1) patients with radioactive iodine-refractory differentiated thyroid cancer (RAI-refractory DTC) to LENVIMA (n=261) or placebo (n=131) [*see Clinical Studies (14)*]. The median treatment duration was 16.1 months for LENVIMA and 3.9 months for placebo. Among 261 patients who received LENVIMA in Study 1, median age was 64 years, 52% were women, 80% were White, 18% were Asian, and 2% were Black; 4% identified themselves as having Hispanic or Latino ethnicity.

In Study 1, the most common adverse reactions observed in LENVIMA-treated patients (greater than or equal to 30%) were, in order of decreasing frequency, hypertension, fatigue, diarrhea, arthralgia/myalgia, decreased appetite, weight decreased, nausea, stomatitis, headache, vomiting, proteinuria, palmar-plantar erythrodysesthesia (PPE) syndrome, abdominal pain, and dysphonia. The most common serious adverse reactions (at least 2%) were pneumonia (4%), hypertension (3%), and dehydration (3%).

Adverse reactions led to dose reductions in 68% of patients receiving LENVIMA and 5% of patients receiving placebo; 18% of patients discontinued LENVIMA and 5% discontinued placebo for adverse reactions. The most common adverse reactions (at least 10%) resulting in dose reductions of LENVIMA were hypertension (13%), proteinuria (11%), decreased appetite (10%), and diarrhea (10%); the most common adverse reactions (at least 1%) resulting in discontinuation of LENVIMA were hypertension (1%) and asthenia (1%).

Table 2 presents the percentage of patients in Study 1 experiencing adverse reactions at a higher rate in LENVIMA-treated patients than patients receiving placebo in the double-blind phase of the DTC study.

Table 2 Adverse Reactions Occurring in Patients with a Between-Group Difference of Greater than or Equal to 5% All Grades or Greater than or Equal to 2% Grades 3 and 4

Adverse Reaction	LENVIMA 24 mg N=261		Placebo N=131	
	All Grades (%)	Grades 3-4 (%)	All Grades (%)	Grades 3-4 (%)
Vascular Disorders				
Hypertension ^a	73	44	16	4
Hypotension	9	2	2	0
Gastrointestinal Disorders				
Diarrhea	67	9	17	0
Nausea	47	2	25	1
Stomatitis ^b	41	5	8	0
Vomiting	36	2	15	0
Abdominal pain ^c	31	2	11	1
Constipation	29	0.4	15	1
Oral pain ^d	25	1	2	0
Dry mouth	17	0.4	8	0
Dyspepsia	13	0.4	4	0
General Disorders and Administration Site Conditions				
Fatigue ^e	67	11	35	4
Edema peripheral	21	0.4	8	0
Musculoskeletal and Connective Tissue Disorders				
Arthralgia/Myalgia ^f	62	5	28	3
Metabolism and Nutrition Disorders				
Weight decreased	51	13	15	1
Decreased appetite	54	7	18	1
Dehydration	9	2	2	1
Nervous System Disorders				
Headache	38	3	11	1
Dysgeusia	18	0	3	0
Dizziness	15	0.4	9	0
Renal and Urinary Disorders				
Proteinuria	34	11	3	0
Skin and Subcutaneous Tissue Disorders				
Palmar-plantar erythrodysesthesia	32	3	1	0
Rash ^g	21	0.4	3	0
Alopecia	12	0	5	0
Hyperkeratosis	7	0	2	0
Respiratory, Thoracic and Mediastinal Disorders				
Dysphonia	31	1	5	0
Cough	24	0	18	0
Epistaxis	12	0	1	0
Psychiatric Disorders				
Insomnia	12	0	3	0
Infections and Infestations				
Dental and oral infections ^h	10	1	1	0
Urinary tract infection	11	1	5	0
Cardiac Disorders				
Electrocardiogram QT prolonged	9	2	2	0

Table 2 Adverse Reactions Occurring in Patients with a Between-Group Difference of Greater than or Equal to 5% All Grades or Greater than or Equal to 2% Grades 3 and 4

Adverse Reaction	LENVIMA 24 mg N=261		Placebo N=131	
	All Grades (%)	Grades 3-4 (%)	All Grades (%)	Grades 3-4 (%)
^a Includes hypertension, hypertensive crisis, increased blood pressure diastolic, and increased blood pressure				
^b Includes aphthous stomatitis, stomatitis, glossitis, mouth ulceration, and mucosal inflammation				
^c Includes abdominal discomfort, abdominal pain, abdominal pain lower, abdominal pain upper, abdominal tenderness, epigastric discomfort, and gastrointestinal pain				
^d Includes oral pain, glossodynia, and oropharyngeal pain				
^e Includes asthenia, fatigue, and malaise				
^f Includes musculoskeletal pain, back pain, pain in extremity, arthralgia, and myalgia				
^g Includes rash macular, rash maculo-papular, rash generalized, and rash				
^h Includes gingivitis, oral infection, parotitis, pericoronitis, periodontitis, sialadenitis, tooth abscess, and tooth infection				

A clinically important adverse reaction occurring more frequently in LENVIMA-treated patients than patients receiving placebo, but with an incidence of less than 5% was pulmonary embolism (3%, including fatal reports vs 2%, respectively).

Table 3 Laboratory Abnormalities with a Difference of at Least $\geq 2\%$ in Grade 3 - 4 Events and at a Higher Incidence in LENVIMA-Treated Patients^a

Laboratory Abnormality	LENVIMA 24 mg N=258 ^b	Placebo N=131 ^b
	Grades 3-4 (%)	Grades 3-4 (%)
Chemistry		
Creatinine increased	3	0
Alanine aminotransferase (ALT) increased	4	0
Aspartate aminotransferase (AST) increased	5	0
Hypocalcemia	9	2
Hypokalemia	6	1
Lipase increased	4	1
Hematology		
Platelet count decreased	2	0

^a With at least 1 grade increase from baseline

^b Subject with at least 1 post baseline laboratory value

In addition the following laboratory abnormalities (all Grades) occurred in greater than 5% of LENVIMA-treated patients and at a rate that was two-fold or higher than in patients who received placebo: hypoalbuminemia, increased alkaline phosphatase, hypomagnesemia, hypoglycemia, hyperbilirubinemia, hypercalcemia, hypercholesterolemia, increased serum amylase, and hyperkalemia.

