4.0 Treatment plan

4.1 Overview

This will be a phase II, non-randomized trial to determine the efficacy and safety of the combination of Eribulin, and lenvatinib in patients with metastatic breast cancer, non-small cell lung cancer and sarcoma. Treatments will be given in cycles of 3 weeks (21 days) and staging scans(CT Scans) will be performed every 2 cycles. Bone scans and MRI brain will be optional. Toxicity assessment will take place after each cycle.

Eribulin will be administered on cycle days 1 and 8; lenvatinib is an orally administered medication which will be given daily throughout each cycle (on cycle 1 lenvatinib will be started on day 2). On days when both drugs are administered, Eribulin will be administered immediately prior to lenvatinib.

Patients will be followed after treatment discontinuation until disease recurrence or death. An evaluable patient for toxicity is any patient who has received at least 1 dose of any of the study drugs. An evaluable patient for efficacy is any patient who has received at least 2 cycles of therapy.

There will be a safety run-in phase. Ten patients will receive lenvatinib at 20 mg daily and Eribulin at 1.4 mg/m² day 1 and day 8 of a 21 day cycle. Eribulin will be given on day 1 and lenvatinib at 20 mg daily will be started on day 2. After completion of 1 cycle of therapy for the first 10 patients the PI will have a teleconference with the medical team at EISAI and decide whether to continue at the same dose or increase the dose to 24 mg daily of lenvatinib and Eribulin at 1.4 mg/m² day 1 and day 8 of a 21 day cycle.

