6.0 Study Parameters

Procedures	Screening & Baseline	Cycle 1	Every cycle ²	Every 2 cycles or at study termination	End of study visit ⁷	Follow-Up ⁶
Tissue procurement ¹	X			X ⁵		
Informed consent	X					
Eribulin administration			X (Days 1 & 8)			
Lenvatinib			X once daily (starting on day 2 of cycle 1)			
Medical history ³	X		X		X	
Physical exam ³	X		X		X	
CBC w/ diff	X ³		X		X	
Comprehensive chemistry panel	X ³		X			
TSH	X		X			
Serum pregnancy test	X					
EKG	X		X ¹⁰			
Blood draw for micro RNA assay ⁹		X			X	

Procedures	Screening & Baseline	Cycle 1	Every cycle ²	Every 2 cycles or at study termination	End of study visit ⁷	Follow-Up ⁶
Urine analysis ¹¹	X			X		
Imaging ⁸	X ⁴			X		
Toxicity assessment			X			
Biopsy				X ⁵		
Survival status						X

¹Archival tissue or a fresh biopsy will be required to procure tissue for study purposes. Biopsy does not need to be repeated for study purposes if archived tissue is available.

Tissue procurement is voluntary

²A cycle is defined as 3 weeks or 21 days (+/- 3 days). Eribulin will be given on cycle days 1 and 8 and lenvatinib starting on day 2 of cycle one and then continuously.

³Pre-study laboratory tests, medical history, and physical exam (including performance status and review of systems) must be completed within 28 days prior to registration.

Pre-study CBC and CCP will be repeated on day 1 prior to treatment administration.

⁴Pre-study imaging must be performed within 28 days prior to registration.

⁵At the initiation and completion of study treatment (or at the time of early withdrawal), tissue samples should be obtained for correlative studies. This is voluntary and will only be done on patients who consent to it.

⁶Patients will be followed every 6 months, at the time of routine clinic visit or via phone, until death, to document disease progression and survival.

⁷Within 30 days of last dose of study medications.

⁸Imaging modality is left to the discretion of the investigator. However the same imaging modality should be used every two cycles to assess disease status.

⁹Blood samples for microRNA assay will be collected on Cycle 1, Day 1 and at the end of treatment.

¹⁰Repeat EKG with every cycle in patients with congestive heart failure, bradyarrhythmias, or those who are taking drugs known to prolong the QT interval, including Class Ia and III antiarrhythmics.

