8.1.2 Phase II

We will use group of n= 30 patients at the MTD. The expected poor response rate is p=0.20 or less, while p>=0.4 or more would be considered successful/good. We intend to proceed by calculating a response rate and providing a 95% confidence interval in the experimental group. This interval will have an approximate half width 2x [0.5/sqrt(30)]= 0.18 or less. We will test the hypothesis that the response rate is larger than 0.2 in the following way: if the lower bound of the one sided 90% exact confidence interval for underlying p is greater than 0.2, we will consider this evidence that p>0.2 i.e. of good response, and worthy of further investigation. Equivalently, using a one sided exact test of H0: p=0.2 versus H1: p>0.2, with power at p=0.4 being over 80%, we have the power analysis below.

Numeric Results for testing H0: P = P0 versus H1: P > P0

Test Statistic: Exact Test

		Given H0	Given H1	Difference	Target	Actual		Reject H0
Power	N	(P0)	(P1)	(P1 - P0)	Alpha	Alpha	Beta	If R>=This
0.8237	30	0.2000	0.4000	0.2000	0.1000	0.0611	0.1763	10

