- determining level of risk (Priority of Audit Level Score – PALS),
- oversight by the Data Safety Monitoring Committee (DSMC), and
- Verification of protocol adherence via annual audit for all Investigator Initiated Studies by the Mays Cancer Center Quality Assurance Division.

Monitoring Progress and Safety

Due to the risks associated with participation in this protocol, the Mays Cancer Center DSMB #2 in conjunction with the Principal Investigator will perform assessment of adverse events, adverse event trends and treatment effects on this study. The Mays Cancer Center DSMB #2 acts as an independent Data Safety Monitoring Board (DSMB) for IIS conducted at Mays Cancer Center. The Mays Cancer Center DSMB #2 will monitor data throughout the duration of a study to determine if continuation of the study is appropriate scientifically and ethically. An additional layer of review is provided by the Mays Cancer Center Data Safety Monitoring Committee (DSMC) who will review DSMB quarterly reports.

Baseline events and adverse events will be captured using the Mays Cancer Center Master Adverse Events Document for each patient using CTCAE V. 4.03 for the grading and attribution of adverse events. Usage of the Mays Cancer Center Master Adverse Events Document centrally documents:

- the event and grades the seriousness of the event,
- if the event was a change from baseline,
- the determination of the relationship between the event and study intervention,
- if the event was part of the normal disease process, and
- What actions were taken as a result of the event.

Safety Definitions:

For this study, the following safety definitions will be applicable:

Adverse Event Definition: An adverse event (AE) is defined as any untoward or unfavorable medical occurrence in a human subject, including any abnormal sign (for example, abnormal physical exam or laboratory finding), symptom, or disease, temporally associated with the subject's participation in the research, whether or not considered related to the subject's participation in the research. For this study, all adverse events will be documented starting with cycle 1 day 1 and ending 30 days after the last dose of study drug is received.

Serious Adverse Event Definition: is any adverse event that:

1. results in death;
2. is life-threatening (places the subject at immediate risk of death from the event as it occurred);
3. results in inpatient hospitalization or prolongation of existing hospitalization;

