Case Report Forms to be submitted during the 21 day DLT Evaluation Period (THIS IS ONLY A REQUIREMENT FOR PHASE I PATIENTS)

- Lab Results *No more than 48 hours after the 21 day DLT period ends*
- Adverse Events Form: *No more than 48 hours after the 21 day DLT period ends*
- Patient Vitals Form: *Each exam conducted during the DLT period, no more than 48 hours after the 21 day DLT period ends*
- Concomitant Medications Form: *Updated as necessary*
- Treatment Cycle Summary Form: *No later than 48 hours after the end of 21 day DLT period*

Case Report Forms to be submitted at the end of each cycle:

- Labs Results Form
- Master Adverse Events Form
- Patient Vitals Form
- Concomitant Medications Form: *Updated as needed*
- Treatment Cycle Summary Form

Case Report Forms to be submitted after every 2 cycles, when disease is assessed

- RECIST Disease Measurements Form: *Complete measurements for each assessment.*

Case Report Forms to be submitted no later than 1 week after End of Treatment Visit:

- Off-treatment Form:
- Patient Vitals Form
- Lab Results Form
- Master Adverse Events Form: *All AEs should be finalized within 30 days of last dose*

Case Report Forms to be completed during follow-up:

- Survival Status Form: Survival status and date of disease progression (if/when applicable) should be completed every 6 months until death.

V. Appendix – Table of Assessments

V. APPENDIX - DATA SUBMISSION TABLE

	Prior to registration	Within 5 days of registration	DLT Period-Only for Phase I Patients	After Each Cycle	After Every 2 cycles	End of Treatment Visit	Follow-Up
Eligibility Form	X						
Informed Consent Form	X						
Pathology Report	X						
On-Study Form		X					
Concomitant Medications Form		X ²		X ⁴			
Patient Vitals Form			X ³	X		X ⁵	
Labs Results Form			X ³	X			
AE Form		X ¹	X ³	X		X ⁵	
Treatment form			X ³	X			
Disease Measurement Form		X		X	X		
Off-Treatment Form						X ⁵	X ⁶
Survival Status Form							X ⁶

1 Should reflect all AEs present at baseline

2 Should reflect medications taken at baseline

3 Should be entered no more than 48 hours after the end of 21 day DLT period

4 Update as required

5 To be entered within 1 week of the end of treatment visit

6 Survival status and date of disease progression will be entered q 6 months until death or until pt withdraw

VI. Appendix SAE Reporting Form

VI. APPENDIX – EISAI SAE REPORT FORM

EISAI CLINICAL STUDY REPORT FORM FOR SERIOUS ADVERSE EVENTS & EVENTS OF SPECIAL INTEREST

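### The end-of-study visit has a CBC but no chemistry panel, so new silent chemistry changes after the last on-treatment draw may be missed, and the two laboratory-form instructions disagree

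*Combined protocol and SAP*

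**What the plan says.** - **Calendar, Section 6.0.** The row "Comprehensive chemistry panel" is marked at screening and every cycle and is blank at the end-of-study visit. The CBC row is marked at that visit, and so is the microRNA blood draw. The visit may fall at any time up to 30 days after the last dose.
- **On-treatment tests, Section 4.2.** Laboratory tests are done within 2 days before days 1 and 8 of all cycles.
- **Who counts, Section 4.1.** "An evaluable patient for toxicity is any patient who has received at least 1 dose of any of the study drugs". Section 5.3.4 gives a similar rule for the toxicity and safety endpoints.
- **Collection window, Appendix III.** "all adverse events will be documented starting with cycle 1 day 1 and ending 30 days after the last dose of study drug is received".
- **Forms, Appendix IV.** Under "Case Report Forms to be submitted no later than 1 week after End of Treatment Visit" the list includes a Lab Results Form. The data submission table in Appendix V marks that form for the DLT period and after each cycle, and leaves the end-of-treatment cell blank.
- **Analysis, Section 8.2.** Descriptive statistics and confidence intervals only. Nothing is said about a laboratory value that was never measured.
- **For contrast, Appendix I.** Table 3 of the reproduced lenvatinib package insert uses 258 of 261 patients as its denominator, with the footnote "Subject with at least 1 post baseline laboratory value". That describes the insert's thyroid-cancer study and is not a rule of this trial.

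**The concern.** Safety is a secondary objective, and Section 5.3.4 undertakes to determine the incidence, nature and severity of adverse events. A new rise in ALT or creatinine, or a fall in calcium, can be silent and is then found only by a blood test. The plan keeps the adverse-event window open for 30 days after treatment and draws blood at the closing visit, but runs only the blood count.

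The package insert shows why chemistry matters for lenvatinib. Six of the seven grade 3-4 laboratory abnormalities in its Table 3 (creatinine, ALT, AST, calcium, potassium, lipase) are chemistry results.

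Two losses follow. Changes that first arise after the last panel have no scheduled test. A patient who stops very early may have no post-baseline panel at all, yet stays in the toxicity denominator. Both push an all-treated laboratory toxicity rate downward if untested is read as unaffected. Separately, sites cannot follow both form instructions. Under the Appendix V table, even the end-of-study CBC that is scheduled has no form to be recorded on.

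**Working it through.** **1. The plan's own figures.** Section 8.1.2 states "We will use group of n= 30 patients at the MTD" and "The expected poor response rate is p=0.20 or less", "with power at p=0.4 being over 80" per cent. With X the number of responders among 30 and rejection at X ≥ 10, the exact binomial tails are:
- alpha = P(X ≥ 10 | p = 0.20) = 0.0611
- power = P(X ≥ 10 | p = 0.40) = 0.8237

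Both match the plan's table. Nothing below changes them. The plan gives no figure for laboratory toxicity to reproduce.

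**2. Time without scheduled chemistry.** Assume a full 21-day final cycle, lenvatinib to day 21, and day 8 tests that include chemistry. Section 4.2 does not name the tests.
- The last panel is drawn between day 6 and day 8.
- On-drug days afterwards: 21 − 8 = 13 to 21 − 6 = 15.
- Adding the 30-day window: 13 + 30 = 43 to 15 + 30 = 45 days.
- With the permitted ±3 days on cycle length, the on-drug part runs from 18 − 8 = 10 to 24 − 6 = 18 days.

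These are calendar days, not missed events. A patient who stops mid-cycle has fewer on-drug days in the gap.

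**3. Patients who stop in cycle 1.** The day 1 chemistry is drawn before treatment (Section 6.0, footnote 3), so it is a baseline value. Lenvatinib starts on day 2, so a panel drawn on day 6 to 8, before that day's dose, follows about 4 to 6 doses. A patient who stops before it has no scheduled post-baseline chemistry.

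**4. Patients with no post-baseline panel.** If m of n treated patients are untested and counted as non-events, expected observed rate = true rate × (n − m)/n. The values of m are assumed. The 9% and 5% rates are borrowed from the insert (hypocalcemia and AST; single agent, 24 mg, thyroid cancer) for illustration only. The run-in has 10 patients, so n is 30 or 40 depending on whether they count within the 30.

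| n | m | true 9% reads | true 5% reads |
|---|---|---|---|
| 30 | 1 | 8.7% | 4.8% |
| 30 | 3 | 8.1% | 4.5% |
| 30 | 5 | 7.5% | 4.2% |
| 40 | 5 | 7.9% | 4.4% |

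**5. Events arising only after the last panel.** If a share f of affected patients first become abnormal then, expected missed patients = n × rate × f. With f assumed at 5% to 30%:
- n = 30: 30 × 0.09 × f = 0.135 to 0.81 at a 9% rate; 30 × 0.05 × f = 0.075 to 0.45 at 5%.
- n = 40: 0.18 to 1.08 at 9%; 0.10 to 0.60 at 5%.

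**6. The same denominator choice in the insert.** 258/261 = 98.9% were tested. A 9% rate on 258 is about 23 patients: 23/258 = 8.9% against 23/261 = 8.8%. When nearly everyone is tested, the choice hardly matters. It matters more in a small trial if several patients stop early.

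**The case against.** The strongest reply is that surveillance is already dense:
- Tests precede days 1 and 8 of every cycle.
- Section 9.0 makes laboratory tests part of adverse-event monitoring and follows abnormal values until they return to baseline, are otherwise explained, or the patient dies.
- Urinalysis is scheduled every 2 cycles or at study termination.
- DLT evaluation is weekly in cycle 1, and laboratory results for the run-in patients are due within 48 hours of the end of the 21-day DLT period, so their cycle 1 coverage may be better than the calendar shows.
- The dominant laboratory toxicity of eribulin in the cited studies is neutropenia, which the end-of-study CBC does detect.

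Most of this stands, and it rules out a broad claim that late liver, renal and calcium toxicity goes unseen. Symptomatic and serious events remain reportable, and abnormalities already found are followed. What it does not cover is a new, silent chemistry change after the final draw. Follow-up of known abnormalities cannot find it, and urinalysis does not measure ALT, creatinine in blood, calcium or potassium.

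Four stronger readings are tempting, and the documents do not support them:
- *Untested values are scored as absent.* No section says so. It is only the default effect of an all-treated denominator.
- *The gap is 50 days.* That takes chemistry on day 1 only. The calendar says every cycle without naming a day, and Section 4.2 specifies day 8 as well.
- *The gap falls where toxicity is most likely, because patients stop for toxicity.* A patient stopped for a laboratory toxicity has already had it detected. Section 4.7 also lists progression and withdrawal, and no distribution of stopping reasons is given.
- *The CBC sees only a small fraction of the label's laboratory signal, by summing the Table 3 percentages.* Those percentages can overlap within a patient, they leave out eribulin, and the contents of the chemistry panel are never listed.

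The different denominator in the insert is not itself an error either. No comparison with it is planned, and the insert warns against comparing rates across trials.

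**Conclusion.** The point holds as a cheap improvement. Following the calendar leaves about 13 to 15 on-drug days of a full final cycle, plus the 30-day window, without scheduled chemistry. New asymptomatic ALT, AST, creatinine, calcium or potassium changes in that time may be missed. The conflict between Appendix IV and the Appendix V table is plain on the page and needs reconciling regardless of any bias.

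The size cannot be derived from the documents. On the assumed inputs it is modest: at most 1.5 percentage points on a 9% rate with 5 of 30 patients untested, and about one missed patient or fewer from late-arising changes. This rests on full cycles, on day 8 tests that include chemistry, on the insert's rates as illustration, and on untested patients being counted as non-events. The response-rate test and its operating characteristics are untouched.

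**What to change.** 1. In Section 6.0, mark the comprehensive chemistry panel at the end-of-study visit.
2. In the Appendix V table, mark the Lab Results Form at the end-of-treatment visit so that it matches Appendix IV.
3. In Section 8.2, add one sentence: each laboratory toxicity will be reported over the patients with at least one post-baseline value for that test, with that number shown, next to the rate over all treated patients.

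The cost is one assay per patient on a visit that already draws blood, one table cell and one sentence. Laboratory toxicity rates may look slightly less favourable. The added panel narrows the gap without fully closing it. If the visit falls on the day of the last dose, the panel covers the 13 to 15 on-drug days and leaves the 30 days after. A single later panel can still miss a change that has already resolved.
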